CNS	central nervous system
COMIRB	Colorado Multiple Institutional Review Board
CR	Complete Response
CrCl	creatinine clearance
CRF	case report form
СТ	computed tomography
CTCAE	Common Terminology Criteria for Adverse Events
CTL	cytolytic T-lymphocyte
CU	University of Colorado
DISC	University of Colorado-Denver Development and Informatics Service Center
DKA	diabetic ketoacidosis
dL	Deciliter
DSM	data and safety monitoring
DSMC	Data and Safety Monitoring Committee
ECI	event of clinical interest
ECOG	Eastern Cooperative Oncology Group
EOT	End of Treatment
EPO	Erythropoietin
ERC	Ethics Resource Center
FDA	Food and Drug Administration
FDAAA	Food and Drug Administration Amendments Act
FDAMA	Food and Drug Administration Modernization Act
FSH	follicle-stimulating hormone
g	Gram
GCP	Good Clinical Practice
GFR	glomerular filtration rate
GI	Gastrointestinal
GM-CSF	granulocyte-macrophage colony stimulating factor
HCG	human chorionic gonadotropin

HIV	Human Immunodeficiency Virus
HLA	human leukocyte antigen
ICH	International Conference on Harmonization
IEC	Institutional Ethics Committee
IFM	Interferon
IL	Interleukin
INR	International Normalized Ratio
IRB	Institutional Review Board
IUD	intrauterine device
IV	Intravenous
kg	Kilogram
L	Liter
m	Meter
mAb	monocolonal antibody
mcL	Microliter
MDSC	myeloid-derived suppressor cell
mg	Milligram
mL	Milliliter
mmol	Millimolar
MRI	magnetic resonance imaging
NCI	National Cancer Institute
NSAID	non-steroidal anti-inflammatory drug
NSCLC	non-small cell lung cancer
OTC	over-the-counter
PBMC	peripheral blood mononuclear cell
PCR	polymerase chain reaction
PI	principal investigator
РК	Pharmacokinetics
ро	by mouth
PT	prothrombin time
Q3W	every three weeks
RA-APL	retinoic acid-acute promyelocytic leukemia
RP2D	Recommended Phase 2 dose
SAE	serious adverse event
SGOT	serum glutamic oxaloacetic transaminase
SGPT	serum glutamic pyruvic transaminase
T1DM	Type 1 diabetes mellitus
TB	Tuberculosis
TSH	thyroid-stimulating hormone
UAP	unanticipated problem
UCCC	University of Colorado Cancer Center
ULN	upper limit of normal
US	United States

1.0 PROTOCOL/TRIAL SUMMARY

Protocol Title	Pembrolizumab and All-Trans Retinoic Acid Combination
Protocol Number	16-1080
Trial Objectives:	Objectives:
	Primary Objective
	To identify the MTD and RP2D of the combination of pembrolizumab and ATRA.
	Secondary Objective
	• Describe the safety and toxicity of combined treatment with pembrolizumab and all-trans retinoic acid (ATRA) [brand name VESANOID] in melanoma patients.
	• To assess the anti-tumor activity of the combination of pembrolizumab and all-trans retinoic acid (ATRA) [brand name VESANOID] in melanoma patients.
	Exploratory Objective
	To determine the clinical outcomes with tumor-specific T cell responses.
Trial Efficacy Endpoints:	 Manipulation of MDSC subsets. Progression-free survival.
Trial Population:	24 subjects to be treated
	• Male and female subjects
	• Ages 18-100
Trial Phase	I/IB
Clinical Indication	Stage IV Melanoma
Trial Type	Interventional
Type of Control	N/A
Description of Study Drug(s)	Pembrolizumab (Keytruda ®) will be administered Intravenous (IV) and Vesanoid will be administered orally.
Trial Blinding	Open Label Clinical Trial
Treatment Groups	One
Number of Trial Subjects	24

Estimated Enrollment Period	1 year
Estimated Duration of Trial	5 years
Duration of Subject Participation	2 years
Estimated Average Length of Treatment Per Patient	VESANOID will be administered over 12 weeks. Pembrolizumab will be administered every 3 weeks until progression of disease, intolerance of therapy, or for up to two years.

This is a multi-center study to be conducted at the University of Colorado Cancer Center (UCHealth central campus) and Poudre Valley Hospital (UCHealth north campus). A complete and current listing of investigators, research personnel, and research facilities participating in this study will be maintained throughout the duration of this study on applicable study required forms such as an *FDA Form 1572*, the *COMIRB Research Personnel Form*, and/or a *UCCC Protocol Contact List*, incorporated herein by reference.

2.0 TRIAL DESIGN

2.1 Trial Design

This is a Phase I/Ib investigator-initiated open label trial of the combination of VESANOID and pembrolizumab treatment.

A total of 24 evaluable patients will be recruited into the study. All the patients will receive 200mg Q3W pembrolizumab treatment plus the supplemental treatment of 150 mg/m² VESANOID orally for 3 days surrounding each of the first four infusions of pembrolizumab (day -1, day 0, day +1) for a total of 12 days of VESANOID treatment (Section 2.2 *Trial Schema/Diagram*).

To closely monitor DLTs, subjects will be recruited into the study using a cohort size of 6. The toxicity monitoring design is to inform de-escalation decisions based on safety if needed. DLTs will be assessed during the DLT assessment window of 21 days following the first dose of Vesanoid and Pembrolizumab (Cycle 1 Day 0 to Cycle 2 Day 0). Patients who withdraw from the study prior to completing the DLT assessment window for any reason other than a DLT will be replaced. See Section 6.1.1.2.3 for DLT definition.

After the first 6 subjects in cohort 1 complete the DLT period, the Sponsor-Investigator will review data pertaining to the dose de-escalation decision. Available adverse event data and laboratory assessments will be used to determine whether the Vesanoid dose should be continued at 150 mg/m^2 or whether the Vesanoid dose should be de-escalated to 100 mg/m^2 in the subsequent six subjects to be enrolled in cohort 2.

Dose de-escalation will proceed in accordance with the following rules:

- 6 patients will be treated in cohort 1.
 - If 0-2 patients experience a DLT in cohort 1, the Vesanoid dose will be maintained.
 - \circ If \geq 3 patients in cohort 1 experience a DLT, then dose de-escalation of Vesanoid will proceed.
- 6 additional patients will be treated in cohort 2 at either the starting Vesanoid dose (150 mg/m²) or the reduced Vesanoid dose (100 mg/m²).
 - If 0-2 patients experience a DLT in cohort 2, the Vesanoid dose will be maintained.
 - If \geq 3 patients in cohort 2 experience a DLT, then the study will stop.
- If it is determined that the dose will be maintained from Cohort 2, then an additional cohort (cohort 3) of up to 12 patients (depending on the number of patients required to achieve the enrollment goal of 24 patients, but not to exceed 30 patients) will be treated at either the starting Vesanoid dose (150 mg/m²), or the reduced Vesanoid dose (100 mg/m²).

This trial will be conducted in compliance with this protocol, Good Clinical Practice, and local and federal regulations.

Anticipated total number of enrolled research subjects: up to 30 to allow for screen fails or withdrawals

Anticipated number to complete study: 24 (who receive at least one dose of VESANOID and Pembrolizumab)

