2.2 Trial Schema/Diagram

Proposed schedule for treatment and blood draws.

Figure 1. Diagram of the treatment and blood draw schedule for this study. Patients will receive pembrolizumab infusions every three weeks. Patients will also receive 3 days of VESANOID treatment surrounding each of the first 4 infusions of pembrolizumab, beginning one day prior to the infusion (a total of 12 days of VESANOID). Six tubes of peripheral blood (for a total of approximately 40 ml) will be drawn at enrollment, at the 2rd and 4th infusions, and within 60 days of the final VESANOID dose for additional functional experiments.

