The choice of the 200 mg Q3W as an appropriate dose for the switch to fixed dosing is based on simulations performed using the population PK model of pembrolizumab showing that the fixed dose of 200 mg every 3 weeks will provide exposures that 1) are optimally consistent with those obtained with the 2 mg/kg dose every 3 weeks, 2) will maintain individual patient exposures in the exposure range established in melanoma as associated with maximal efficacy response and 3) will maintain individual patients exposure range established in melanoma that are well tolerated and safe.

A fixed dose regimen will simplify the dosing regimen to be more convenient for physicians and to reduce potential for dosing errors. A fixed dosing scheme will also reduce complexity in the logistical chain at treatment facilities and reduce wastage.

All the patients will receive 200mg Q3W pembrolizumab treatment plus the supplemental treatment of 150 mg/m² VESANOID orally for 3 days surrounding each of the first four infusions of pembrolizumab (day -1, day 0, day +1) for a total of 12 days of VESANOID treatment (Section 2.2 *Trial Schema/Diagram*). The total daily dose of VESANOID may be taken anytime on the day before the pembrolizumab infusion (day -1) according to the patient's preferences, prior to the pembrolizumab infusion on the day of the infusion (day 0), and anytime on the day after the pembrolizumab infusion (day 1) according to the patient's preferences.

VESANOID Dose Selection

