6.0 STUDY AGENT AND TRIAL TREATMENT

6.1 Study Drug Description and Trial Treatments

The treatment to be used in this trial is outlined below in Table 2

Drug	Dose/	Dose	Route of	Regimen/	Use
	Potency	Frequency	Administration	Treatment Period	
Pembrolizumab	200 mg	Q3W	IV infusion	Day 0 of each 3 week cycle	Standard agent
All-trans retinoic acid	150 mg/m ²	Q3W	Oral	Day -1, 0, and 1 of each 3 week cycle (first four cycles)	Experimental agent

Table 2 Trial Treatment

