The trial stopping criteria outlined in the table found in Section 6.6.5 - *Toxicity and Study Discontinuation Criteria* will be followed to avoid posing undue risk to additional patients. Twenty four (24) patients will potentially be recruited to further evaluate safety and assess preliminary efficacy.

Dose limiting toxicities are defined according to the AE profile observed during the first cycle (Cycle 1 Day 0 to Cycle 2 Day 0) of study drug administration. All AEs should be considered possibly related to the study drug unless such relationship can be definitively excluded.

Toxicity will be evaluated according to NCI CTCAE Version 4.0. A DLT will be defined as any of the following events that are considered by the investigator to be at least possibly related to treatment with Vesanoid and Pembrolizumab:

- 1. Any >= grade 3 non-hematologic toxicity related to VESANOID, > = grade 4 hematologic toxicity related to VESANOID or other grade VESANOID related adverse events that lead to treatment discontinuation. An exception is VESANOID related headache not optimally managed with supportive care therapies (acetaminophen or non-steroidal antiinflammatory medication) or that does not resolve within 72 hours of stopping the VESANOID. A patient's choice to stop all VESANOID, with or without a dose reduction, due to headache alone will not be considered a dose limiting toxicity.
- 2. Any >= grade 3 toxicity related to Pembrolizumab.

Dose Level	Number of Patients	Vesanoid	Pembrolizumab
-1	6	$100 \text{ mg/m}^2 \text{ PO on days -1, 0, and 1}$ every 3 weeks for the first 4 cycles	200 mg IV on Day 0 every 3 weeks
1 (Starting Dose)	6	150 mg/m ² PO on days -1, 0, and 1 every 3 weeks for the first 4 cycles	200 mg IV on Day 0 every 3 weeks

The dose levels will be as follows:

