6.1.2 Timing of Dose Administration

Trial treatment with Pembrolizumab should be administered on Day 0 of each cycle after all procedures/assessments have been completed as detailed on the *Trial Schedule of Events Chart (Section 7.1)*. All trial treatments will be administered on an outpatient basis. VESANOID will be administered on day -1, 0 and 1 with each of the first four cycles of Pembrolizumab. VESANOID will be administered twice a day (75mg/m² each dose for a total dose of 150mg/m²).

Pembrolizumab 200 mg will be administered as a 30-minute IV infusion every 3 weeks. Given the variability of infusion pumps from site to site, a window of -10 minutes and +10 minutes is permitted (i.e., infusion time is 30 minutes: -10 min/+10 min).

The Pharmacy Manual and investigational brochure contains specific instructions for the preparation of the pembrolizumab infusion fluid and administration of infusion solution.

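### The DLT window is labelled from Cycle 1 Day 0, but Vesanoid starts the day before, so a qualifying event confined to Day -1 falls outside the DLT count (minor)

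*Combined protocol and SAP*

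**What the plan says.** **The window.** Section 2.1 (Trial Design) sets a "window of 21 days following the first dose of Vesanoid and Pembrolizumab (Cycle 1 Day 0 to Cycle 2 Day 0"). The DLT definition in section 6.1.1.2.3 repeats the labels: "Dose limiting toxicities are defined according to the AE profile observed during the first cycle (Cycle 1 Day 0 to Cycle 2 Day 0").

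**The dosing.** Section 2.1 gives Vesanoid on days -1, 0 and +1 around each of the first four infusions. Section 2.2 describes it as "beginning one day prior to the infusion (a total of 12 days of VESANOID"). Table 2 in section 6.1 lists "Day -1, 0, and 1 of each 3 week cycle (first four cycles"), and section 6.1.2 says "VESANOID will be administered on day -1, 0 and 1 with each of the first four cycles of Pembrolizumab". Footnote a to the schedule in section 7.1 has the Cycle 1 supply dispensed in clinic on Cycle 1 Day -1. Pembrolizumab is first given on Day 0.

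**The use of the count.** Under section 2.1, three or more patients with a DLT out of six lead to de-escalation after cohort 1 and to a study stop after cohort 2. On replacement it says: "Patients who withdraw from the study prior to completing the DLT assessment window for any reason other than a DLT will be replaced". Table 5 in section 6.6.5 gives the same threshold, but the text above it defines toxicity as adverse events of grade 3 or higher and attaches no time window.

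**The concern.** Vesanoid is the experimental agent, and one of its three Cycle 1 dosing days comes before the window that is meant to judge it. Read literally, the labels exclude a qualifying event that begins and ends on Day -1. The replacement rule adds to this: a patient who withdraws because of such an event has, by the labels, left for a reason other than a DLT, so another patient takes the place.

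The count out of six drives de-escalation and study stopping, and it supports the primary objective of identifying the MTD and RP2D. Leaving out Day -1 can only lower that count. The sections also disagree on whether the event matters: sections 2.1 and 6.1.1.2.3 leave it out by their labels, while section 6.6.5 could take it in. Two readers could classify the same patient differently.

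**Working it through.** **1. Reproduce the stated length.** Set Cycle 1 Day 0 = 0. On a three-week cycle, Cycle 2 Day 0 = 21.

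- Cycle 1 Day 0 to Cycle 2 Day 0: 21 - 0 = 21 days, as section 2.1 states.
- Cycle 1 Day -1 to Cycle 2 Day 0: 21 - (-1) = 22 days.
- 21 days counted from Cycle 1 Day -1: -1 + 21 = 20, which is Cycle 2 Day -1.

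The stated 21 days and the printed labels therefore agree only if the clock starts once both drugs have been given. If it starts at the first Vesanoid dose, the labels are wrong at both ends.

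**2. Vesanoid days inside the labelled window.** With Cycle 2 on schedule, the first two courses fall on days -1, 0, 1 and 20, 21, 22. Days 0, 1, 20 and 21 lie in the window (closing day included). So the window takes in Cycle 2 Day -1 (day 20) and leaves out Cycle 1 Day -1.

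**3. Does any section bring Day -1 in?** Table 2 treats Day -1 as part of a cycle, so the words about the first cycle in section 6.1.1.2.3 might reach it, but the parenthesis there limits them to Day 0 onward. No other section extends the DLT window.

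**4. How wide is the gap?** Drug is dispensed in clinic on Day -1, and section 4.2.2 adds: "The total daily dose of VESANOID may be taken anytime on the day before the pembrolizumab infusion (day -1"). The uncounted exposure is at most part of one day. An event still present on Day 0 is observed in the window and can count. Section 6.1.1.2.3 also has an exception for Vesanoid-related headache and says that a patient's choice to stop for headache alone is not a DLT. Section 4.2.2 names headache as the significant common side effect in the team's earlier trial of Vesanoid with ipilimumab.

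**5. Illustration only.** The documents do not say what share of DLTs would be confined to Day -1. With X the number of patients with a DLT out of 6:

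P(X ≥ 3) = 1 - Σ(k = 0 to 2) C(6,k) p^k (1-p)^(6-k)

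At the 33% target rate (section 8.0) this is 1 - (0.0905 + 0.2673 + 0.3292) = 0.313. At 24%, which is the 14% + 10% of section 6.6.5, it is 0.154. Let d be the loss in the counted rate. A patient who stays as a non-DLT gives p - d; one who is replaced gives (p - d)/(1 - d).

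| Base rate | Assumed share confined to Day -1 | P(X ≥ 3) |
|---|---|---|
| 24% | 5% to 10% of the 10 added points (d = 0.5 to 1 point) | 0.148 to 0.139 |
| 33% | same d | 0.306 to 0.294 |
| 33% | 5% to 10% of 33 - 14 = 19 points (d = 0.95 to 1.9 points) | 0.301 to 0.276 |
| 33% | 5% to 20% of all DLTs, patient stays | 0.281 to 0.192 |

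The first three rows span both treatments of the patient. The last row is severe, because a pembrolizumab-related DLT cannot precede the first infusion. The spread between rows comes from the assumption and not from the documents. In addition, section 6.6.5 gives its rates without a time period, so they are not Cycle 1 DLT rates.

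**The case against.** The strongest defence is that nothing is inconsistent. The trial studies the combination, and a window that opens when both drugs have been given fits both the labels and the 21 days. That reading is available, and it could be a deliberate choice. It would still leave first exposure to the experimental agent outside the count while Cycle 2 Day -1 is inside, and the documents give no reason for that.

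It also leaves open how to count a patient with a qualifying Vesanoid event who is taken off study before the first infusion. Section 6.6.1 allows removal for an untoward effect. The expected completers in section 2.1 are those who received both drugs: "Anticipated number to complete study: 24 (who receive at least one dose of VESANOID and Pembrolizumab").

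Three stronger readings are tempting, and the documents do not support them:

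- A reader might infer that Day -1 toxicity goes unseen. It does not. The cohort review in section 2.1 uses available adverse event and laboratory data, section 10.3.1 has toxicity addressed in real time, and the safety analyses in section 8.0 include everyone who received any protocol therapy.
- A reader might infer that the 3-of-6 rule cannot take in a Day -1 event at all. Section 6.6.5 states the rule for adverse events of grade 3 or higher with no window, and section 6.1.1.2.3 says those criteria will be followed. On that text a grade 3 event on Day -1 could count. The fault is that the sections differ.
- A reader might infer that sections 2.1 and 6.1.1.2.3 contradict each other on the window. They agree. The mismatch is with the dosing schedule.

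**Conclusion.** The point stands as a minor correction. As labelled, the DLT window starts after the first Vesanoid dose, no section brings Cycle 1 Day -1 into the DLT count, and section 6.6.5 describes the same threshold without that window. The direction is certain: the omission can only lower the count. The size is unknown and probably small, since the event must both start and resolve within part of one day and the headache exception narrows the gap further. The probabilities in the table show how the rule responds to an assumed share. They should not be read as an estimate of bias in the de-escalation or stopping decision.

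**What to change.** 1. In sections 2.1 and 6.1.1.2.3, open the DLT window at the first dose of either study drug (Cycle 1 Day -1) and keep the end at Cycle 2 Day 0.
2. In section 2.1, change the 21 days to match: from Day -1 through 21 days after the first infusion, 22 days in all.
3. State that a patient with a qualifying event in this window is counted as a DLT and not replaced, whether or not pembrolizumab was given.
4. In section 6.6.5, make Table 5 refer to the same DLT definition and window, so that one count serves both statements of the rule.

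The cost is wording in three sections. No visit is added, since drug is already dispensed in clinic on Cycle 1 Day -1. The downside is that the counted DLT rate may be slightly higher, which makes reaching three of six slightly more likely.

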6.6.5 Toxicity and Study Discontinuation Criteria

The trial stopping criteria outlined in the Calculated Trial Stopping Criteria (Table 5) below will be followed to avoid posing undue risk to additional patients. Twenty-four patients will potentially be recruited in our study to evaluate DLTs and suggest RP2D. Toxicity is defined as AEs of grade 3 or higher. Historical data of similar patients show an overall grade 3 or 4 toxicity rate of approximately 14% for pembrolizumab treatment alone. It is estimated that the current trial (the combination) may increase toxicity rates an additional 10% compared to pembrolizumab alone. The DSMC will have oversight responsibilities for reviewing toxicities in patients associated with this trial.

Number of Patients	Stopping Criteria	Dosing Action
6 (Cohort 1)	>=3	Dose de-escalate in Cohort 2 (dose level -1)
6 (Cohort 2)	>=3	Study Stop

Table 5 Calculated Trial Stopping Criteria

If the grade 3 or 4 toxicity exceeds 33% the stopping criteria, the next 6 enrolled patients will be put on the lower dose.

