8.0 STATISTICAL ANALYSIS PLAN

The primary goal of the study is to characterize the safety and establish the recommended phase 2 dose (RP2D) and preliminary efficacy evaluation with a total of 24 evaluable subjects. A modified 3+3 design with a cohort size of 6 with a continuous toxicity monitoring. The design is to inform de-escalation decisions based on safety if needed. For the purposes of this trial, a target toxicity rate of approximately 33% will be used to establish the RP2D. Table 7 below provides the probability of detecting the number of DLTs based on true toxicity rates with 24 subjects:

Table 7 Number of DLTs and the Corresponding Cumulative Probability for SeveralToxicity Rates with 24 Subjects

True toxicity rate (%)	Corresponding Number of	Cumulative Probability for
	DLTs (# DLT)	Detecting #DLT
20	5	0.66
25	6	0.56
30	7	0.56
35	8	0.53
40	10	0.65

Safety Analyses

All patients who received any protocol therapy will be employed for safety analyses. Patient incidence of all treatment-emergent AEs will be tabulated by dose and system organ class and preferred term. Tables of fatal adverse events, serious adverse events, treatmentrelated AEs, and adverse events leading to withdrawal from investigation product will also be provided. The MedDRA will be used to code adverse events and the NCI CTCAE version 4.0 will be used to grade severity of adverse events and laboratory toxicities.

Summary statistic will be provided for total number of subjects treated under each dose, average dose administered, and duration of treatment.

For select laboratory parameters, changes of laboratory values over time (eg, change from baseline summary statistics), grade shifts in laboratory values from baseline to worst onstudy value, and grade 3 or higher laboratory toxicities will be summarized. The ECG measurements from this study will be performed as per standard of care for routine safety monitoring.

Efficacy analysis

The efficacy analysis population consists of all subjects who receive at least one cycle treatment (3-day doses of study treatment).

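### The cohort 1 dose review waits for six completed DLT windows, so the plan does not bar new starts at 150 mg/m² after a third DLT has already fixed de-escalation

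*Combined protocol and SAP*

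**What the plan says.** Section 2.1 recruits in cohorts of six with a 21-day DLT window and fixes the cohort 1 review point: "After the first 6 subjects in cohort 1 complete the DLT period, the Sponsor-Investigator will review data pertaining to the dose de-escalation decision". It also states that "6 patients will be treated in cohort 1". With zero to two DLTs the Vesanoid dose is kept; with three or more it falls from 150 to 100 mg/m² for the six subjects of cohort 2. Table 5 in Section 6.6.5 agrees: six patients in cohort 1, a limit of three, de-escalation in cohort 2. For cohort 2, if three or more "patients in cohort 2 experience a DLT, then the study will stop". Otherwise there follows "an additional cohort (cohort 3) of up to 12 patients".

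Two further sentences bear on timing. Below Table 5, Section 6.6.5 adds: "If the grade 3 or 4 toxicity exceeds 33% the stopping criteria, the next 6 enrolled patients will be put on the lower dose". Section 8 describes the design as "A modified 3+3 design with a cohort size of 6 with a continuous toxicity monitoring", with no boundary or action before six patients.

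General safeguards also exist:
- The treating oncologist and principal investigator may lower or stop Vesanoid (Section 6.1.1.2.2).
- The principal investigator is told of every adverse event (Section 6.1.1.2.3).
- The trial may end early for a health hazard (Section 6.6.6).
- Toxicity is handled in real time and at weekly meetings, and the DSMC can suspend the trial (Section 10.3.1).

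**The concern.** The rule is a count of three. Once the third DLT has occurred, later cohort 1 patients cannot change the Table 5 outcome, provided the three attributions stand. Someone who starts at 150 mg/m² after that point receives a dose that the protocol's own rule is about to drop. Section 6.6.5 says the criteria "will be followed to avoid posing undue risk to additional patients", and such a patient is one of those additional patients.

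Whether that start is held back rests on judgement, because no text closes cohort 1 at the third DLT, staggers starts or suspends entry on a count. At stake is the avoidable exposure of at most three evaluable patients, plus any replacements. The validity of the dose decision is not affected. A late starter would still add safety and MDSC data.

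**Working it through.** **Plan's own figure.** There is none to reproduce. Table 7 in Section 8 concerns DLT counts among 24 subjects; no operating characteristics are given for the three-of-six rule.

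**Inputs from the document**
- Cohort size 6, limit 3, window 21 days (Section 2.1, Table 5).
- Target toxicity rate about 33% (Section 8).
- Section 6.6.5: "Historical data of similar patients show an overall grade 3 or 4 toxicity rate of approximately 14% for pembrolizumab treatment alone". The combination may add 10%, read here as percentage points: 14% + 10% = 24%. These are overall grade 3 or 4 rates, not cycle 1 DLT rates, so the true 21-day rate may be lower.
- 24 patients in an estimated one-year enrolment period (Section 1.0): 365/24 = 15.2 days between starts.

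**Step 1: upper bound.** Suppose each patient's window closes before the next patient starts. For true DLT rate p, the third DLT occurs at patient k with probability

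P(k) = C(k−1, 2) p³ (1−p)^(k−3), for k = 3, 4, 5, 6.

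At least one cohort 1 place is then still open when k ≤ 5. At p = 0.33, p³ = 0.0359, so:
- P(3) = 0.0359
- P(4) = 3 × 0.0359 × 0.67 = 0.0722
- P(5) = 6 × 0.0359 × 0.67² = 0.0968
- P(6) = 10 × 0.0359 × 0.67³ = 0.1081

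The chance of at least one open place is 0.0359 + 0.0722 + 0.0968 = 0.205 (0.20496 before rounding). The chance of de-escalation is the sum of all four terms, 0.313. The mean number of later starts is 3 × 0.0359 + 2 × 0.0722 + 1 × 0.0968 = 0.349. Given de-escalation, the chance of at least one later start is 0.20496/0.31305 = 0.655.

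| True DLT rate | P(at least one later start), upper bound | Mean later starts | P(de-escalation) | P(later start given de-escalation), upper bound |
|---|---|---|---|---|
| 14% | 0.022 | 0.035 | 0.039 | 0.558 |
| 24% | 0.093 | 0.152 | 0.154 | 0.606 |
| 33% | 0.205 | 0.349 | 0.313 | 0.655 |

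**Step 2: allow for accrual.** Entry spacing and DLT onset are not in the document, so these are assumptions. Onset is taken as uniform over 21 days, and a start counts if it falls after the third DLT. Simulated chance of at least one such start:

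| Entry pattern | 14% | 24% | 33% |
|---|---|---|---|
| Random (exponential) gaps, mean 15.2 days | 1.5% | 6.5% | 14% |
| Same, with 7 days to recognise each DLT | 1.1% | 4.9% | 11% |
| Even 15-day gaps | 2% | 8% | 18% |
| Even 7-day gaps | 1% | 5% | 11% |
| All six start together | 0 | 0 | 0 |

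**Step 3: does another sentence supply the trigger?** The 33% sentence sits under Table 5, whose rows count six patients. Read that way, three DLTs give 3/6 = 50%, above 33%, in agreement with Section 2.1 but also acting only at six. Read as a running rate it would fire at 1/1 or 1/2, which no section intends. Under either reading, 2/6 = 33.3% is fractionally above 33% although Table 5 keeps the dose there. So the sentence does not give a usable stop at the third DLT.

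**The case against.** The strongest reply is that reviewing a full cohort of six is a coherent design choice, stated consistently in Section 2.1 and Table 5. That stands. A reader might infer that the timing is unclear or that the sections contradict each other. The documents do not support this: Section 2.1 names the review point, and the 33% sentence can be read with Table 5's denominator. The 2/6 mismatch is a matter of rounding against a target that Section 8 itself calls approximate.

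A reader might also infer that the plan obliges sites to keep dosing after a third DLT. It does not. The review sentence schedules a review without forbidding an earlier pause, and the safeguards in Sections 6.1.1.2.2, 6.1.1.2.3, 6.6.6 and 10.3.1 give real authority to act. What they lack is a count that triggers action.

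Nor can the same wait be read into cohort 2. Its stopping rule carries no wait for six patients and no stated timing, so there the point is only a clarification.

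Finally, DLT status depends on the investigator's judgement of relatedness, so a third DLT at onset may not be final. That is fair, and the fix should refer to confirmed DLTs.

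**Conclusion.** The point holds as a small patient-safety improvement, not a design failure. As written, the plan leaves open up to three evaluable starts at 150 mg/m² after its own rule has settled on de-escalation. The chance that this happens at all is at most about 2%, 9% and 20% at true DLT rates of 14%, 24% and 33%, and nearer 1.5%, 6.5% and 14% under random entry averaging 15 days.

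De-escalation itself is uncommon at the anticipated rates (4% and 15%, rising to 31% at the target). When it does occur, an open place at the third DLT is more likely than not under the upper bound: 56%, 61% and 65%. The accrual-based figures are lower and depend on assumed spacing and onset; the upper bounds depend only on the DLT rate and on patients being independent.

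**What to change.** State the trigger once in Section 2.1, in place of the current review sentence, and cross-refer to it from Sections 6.6.5 and 8. Suggested wording:

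> In cohorts 1 and 2, new starts at the current Vesanoid dose are paused and the Sponsor-Investigator holds the Table 5 review at the third confirmed DLT, or when six evaluable patients (replacements included) have each completed the 21-day window or had a DLT, whichever comes first. Patients already started continue their window.

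Consequential edits:
- Change the cohort 1 and 2 sizes to up to six evaluable patients in Section 2.1, Table 5 and the dose-level table in Section 6.1.1.2.3.
- Tie the 33% sentence in Section 6.6.5 to the Table 5 limit of three or more DLTs.
- Let cohort 3 exceed 12 by the number of unused cohort 1 places. Otherwise, closing cohort 1 at three, four or five gives 3 + 6 + 12 = 21, 4 + 6 + 12 = 22 or 5 + 6 + 12 = 23 patients instead of 24. Cohort 3 would need 15, 14 or 13, and the total of 24 stays within the limit of 30.

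The cost is these wording changes and slightly less safety and MDSC data at the dose being dropped. Patients after the third confirmed DLT cannot alter a three-or-more rule, so the probability of each Table 5 decision is unchanged.
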